## 10.3. Adverse Events / Adverse Drug Reactions

Adverse events (AEs) will be coded using MedDRA Version 25.0.

Treatment-emergent AEs (TEAEs) is defined as AEs with an onset date on or after the first dose date of study treatment. Partially missing date will be handled using the algorithm described in Section 6.3. AE

related to study drug is defined as AE with a relationship to study drug reported as 'Reasonable Possibility' or missing.

Summary table for adverse events will include the number and percent of subjects and the numbers of events by treatment group and by System Organ Class (SOC) and Preferred Term (PT). SOC and PT within each SOC will be sorted by descending overall frequency. Subjects who have multiple events in the same SOC and the same PT within each SOC will be counted only once in the subject counts, but all events will be considered and presented (if applicable). For summary by maximum severity, subjects who experience multiple occurrences of an AE, the most severe category for each SOC and for each PT within each SOC will be considered in the summary.

The summary tables for following TEAEs will be presented:

- Overall Summary: summary of the number and percentage of subjects reporting TEAEs, TEAEs by
  maximum severity, serious TEAEs, study drug-related TEAEs, drug-related serious TEAE, study
  drug-related TEAEs by maximum severity, treatment-emergent AESI, Confirmed or suspected
  COVID-19 infection, TEAEs leading to study drug withdrawal, TEAEs leading to study drug
  interruption, TEAEs leading to study discontinuation, and TEAEs leading to death
- The total number and incidence of TEAEs by SOC and PT
- The total number and incidence of Serious TEAEs by SOC and PT
- The total number and incidence of TEAEs related to study drug by SOC and PT
- The total number and incidence of serious TEAEs related to study drug by SOC and PT
- The total number and incidence of TEAEs by SOC, PT, and maximum severity
- The total number and incidence of drug-related TEAEs by SOC, PT, and maximum severity
- The total number and incidence of TEAEs leading to temporary interruption of study drug by SOC and PT
- The total number and incidence of TEAEs leading to permanent discontinuation of study drug by SOC and PT
- The total number and incidence of TEAEs leading to study discontinuation by SOC and PT
- The total number and incidence of TEAEs of special interest by SOC and PT
- Most common TEAEs (frequency > 5%) by PT. All TEAEs with a frequency >5% in any treatment group will be presented.

Subject listings will be presented for all AEs, all SAEs, AEs leading to study drug withdrawal, AEs of special interest (AESIs). All AEs will be listed by subject, along with information regarding onset, duration, relationship and severity to study drug, action taken with study drug, treatment of event, and outcome.

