9.7.1 Early Termination Visit

Subjects may discontinue from the study or discontinue the study treatment only and continue to participate in the study.

Subjects who prematurely discontinue from the study should undergo final study assessments according to the following guidelines:

- Subjects discontinued from the study during the treatment period on/before the Week 16 visit should attend an early termination visit.
- A follow-up/final visit is required 12 weeks after the last study drug administration.

Subjects who prematurely discontinue the study drug will be asked to continue participation in the study; however, subjects who discontinue the study drug prior to Week 12 should not be vaccinated. Subjects will be asked to return for all remaining visits and assessments (including daily assessment of pruritus, sleep disturbance, etc). Participation will continue until the subject completes the final study visit or otherwise discontinues study participation.

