No suggestive evidence or arguments can be identified regarding a causal relationship between the study drug or the clinical study protocol procedure and the AE.

Action Taken

The investigator will describe the action taken in the appropriate section of the eCRF, as follows:

- None

This document is confidential.

- Study drug stopped
- Study drug temporarily interrupted
- Concomitant medication (any additions or discontinuations)
- Other, specify

Follow-up of Adverse Events

All investigators should follow-up with subjects with AEs until the event is resolved or until, in the opinion of the investigator, the event is stabilized or determined to be chronic. Details of AE resolution must be documented in the eCRF.

Subjects should be followed up for 12 weeks (\pm 5 days) after receiving the last dose of study drug, and any AEs that occur during this time should be reported according to the procedures outlined above.

Documentation and Reporting of Adverse Events

Adverse events should be reported and documented in accordance with the procedures outlined below. All AEs occurring during the study must be documented on the relevant eCRF pages. The following data should be documented for each AE:

- Description of the symptom event
- Classification of “serious” or “not serious”
- Severity
- Date of first occurrence and date of resolution (if applicable)
- Action taken
- Causal relationship
- Outcome of event (unknown, recovered, not yet recovered, recovered with sequelae, death [with date and cause reported])

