16.6 Safety Analysis

All safety analyses will be conducted on the SAF, by treatment group.

All reported AEs will be coded using the Medical Dictionary for Regulatory Activities (MedDRA), version 22.0 or later. The treatment-emergent period will be defined as the period of time from the first dose date of study treatment through 12 weeks (84 days) after the last dose of study treatment (ie, up to the follow-up visit for completers), or the date of rollover to the LTE study (SPR.118163), whichever is earlier. The incidence of TEAEs (events with onset dates on or after the start of the study drug), drug-related TEAEs, SAEs, TEAEs leading to study drug discontinuation and treatment-emergent AESIs will be included in incidence tables, summarized by System Organ Class (SOC) and Preferred Term (PT). Events with missing onset dates (and no data to suggest the

[figure not shown]
This document is confidential.

event stopped prior to study treatment start) will be included as treatment-emergent. The incidence of TEAEs by severity, counting multiple AEs under SOC and PT for a subject at the maximum severity will be presented. All AEs will be listed by subject, along with information regarding onset, duration, relationship and severity to study drug, action taken with study drug, treatment of event, and outcome.

Clinical laboratory data and vital signs will be summarized using descriptive statistics, including observed values and change from baseline values, as well as numbers of subjects with values outside limits of the normal range, including shifts from baseline at each time point.

Summary tables will be provided for 12-Lead ECG, Physical Examination (Full and Symptom-oriented), ACT, PEF, and Respiratory Exam, by treatment group and visit where appropriate. Listings will also be provided.

[figure not shown]
CCI

This document is confidential.

Page 106 of 133

CCI

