#### 6.2.3. Study period

First treatment date is defined as the date of 1st study drug (Nemolizumab or Placebo) injection.

Last treatment date is defined as the date of last study drug (Nemolizumab or Placebo) injection.

Treatment period is defined as follow:

- Subject completed the treatment: first dose date up to Week 16
- Subject who discontinued the treatment: first dose date up to earliest among:

- o 4 weeks after the last study drug administration
- o the early study termination date if available

Screening period is defined the period before the treatment period.

Follow-up period is defined the period after the treatment period.

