## 6.3. Missing Data

Adverse events and concomitant medications with missing assessment times will have imputed times for the purposes of assessing treatment emergence for AEs or classifying medications into prior/concomitant. However, the assessment times (start date, stop date) without imputation will be presented in the listings.

For the start of a concomitant medication or AE:

- Only the year is reported: If the subject received the first study drug dose in the year reported, then the date of the first dose of study drug will be used as the start date; otherwise, January 1 of the year reported will be used as the start date.
- The month and year are reported: If the subject received the first study drug in the month and year reported, then the date of the first dose of study drug will be used as the start date; otherwise, the first day of the month and year will be used as the start date.
- The time is missing: If the start date is the same as the date the subject started receiving study drug, then the time of the first dose of study drug will be used as the start time; otherwise, 00:00 will be used as the start time.

For the end of a concomitant medication or AE:

- Only the year is reported: The earlier between December 31 of the year reported and the date of the last study contact with the subject will be used as the stop date.
- The month and year are reported: The earlier between the last date of the month and year reported and the date of the final contact with the subject will be used as the stop date.

If an AE has the start date completely missing and the stop date on/after the first dose date of study drug, this AE will be considered as treatment emergent.

If a medication has the stop date completely missing and ongoing tick box in CRF is checked, this medication will be considered as concomitant.

Imputations or calculations for specific efficacy endpoints will be included in the section that describes the analysis of that endpoint.

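### SAP 10.3 omits the end date that protocol 16.6 sets for treatment-emergent adverse events, and SAP 14 does not declare the change

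*SAP*

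**What the plan says.** **Protocol 16.6** defines the treatment-emergent period as the "period of time from the first dose date of study treatment through 12 weeks (84 days) after the last dose of study treatment", "or the date of rollover to the LTE study (SPR.118163), whichever is earlier". The next sentence introduces the tables: "The incidence of TEAEs (events with onset dates on or after the start of the study drug"). An event with no onset date counts as treatment-emergent unless data suggest that it stopped before treatment began.

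**SAP 10.3** defines the same term by its start alone: "Treatment-emergent AEs (TEAEs) is defined as AEs with an onset date on or after the first dose date of study treatment". It refers to SAP 6.3 for partial dates. SAP 6.2.3 names a follow-up period without closing it or tying it to TEAEs: "Follow-up period is defined the period after the treatment period". For a wholly missing onset, SAP 6.3 covers one case: "If an AE has the start date completely missing and the stop date on/after the first dose date of study drug", the event is treatment-emergent.

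**SAP 14** (14.1 to 14.4) lists changes to concomitant medication, secondary endpoint analysis, estimands and vaccine secondary endpoints. It lists nothing on TEAEs.

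**Collection of events.** Protocol 13.1 collects adverse events from consent to the end of the study. It also asks for follow-up to 12 weeks (± 5 days) after the last dose: "any AEs that occur during this time should be reported according to the procedures outlined above". Protocol 9.7.1 keeps early stoppers in view: "Subjects who prematurely discontinue the study drug will be asked to continue participation in the study", returning for all remaining visits and assessments.

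**The concern.** The protocol window is closed and the SAP window is open. A programmer following SAP 10.3 would flag any recorded event with onset on or after first dose, however late. Off-drug events outside the protocol window would then enter the TEAE tables.

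Incidence and severity of adverse events is the safety endpoint (protocol 6.2.2.3). SAP 10.3 reports it as subject counts, percentages and event counts, and no readable text there adjusts for time at risk. The length of the window therefore feeds straight into the reported incidence. If early discontinuation differs between the groups, so does the added time.

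**Working it through.** No power or sample-size formula applies. The check is calendar arithmetic followed by a comparison of texts.

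**Inputs.** Doses at Baseline and Weeks 4, 8 and 12 (protocol Table 2); 84-day bound (protocol 16.6); ± 5 days (protocol 13.1); target days of 113 for Week 16 and 169 for Week 24 (SAP 6.4). Week w falls on study day 7w + 1.

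**Reproducing the protocol's figure.** 12 × 7 = 84 days. The Week 12 dose is on day 7 × 12 + 1 = 85, and 85 + 84 = 169, the Week 24 target. This agrees with the protocol's remark that, for completers, the window runs to the follow-up visit.

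**Time counted by the SAP but not by the protocol, subjects not entering the LTE.** Window end = last dose day + 84. Two cases for last contact bracket the excess:

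| Last dose | Day | Protocol window ends | Excess if followed to Day 169 | Excess if last contact is the later of Day 113 and last dose + 84 |
|---|---|---|---|---|
| Baseline | 1 | 85 | 169 − 85 = 84 | 113 − 85 = 28 |
| Week 4 | 29 | 113 | 169 − 113 = 56 | 113 − 113 = 0 |
| Week 8 | 57 | 141 | 169 − 141 = 28 | 141 − 141 = 0 |
| Week 12 | 85 | 169 | 0 | 0 |

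**Visit tolerance.** A follow-up visit 5 days late falls 84 + 5 = 89 days after the last dose, so up to 5 days lie outside the protocol window even for a completer.

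**LTE entrants.** Entry at Week 16 is 113 − 85 = 28 days after the Week 12 dose. The 12-week reporting period in protocol 13.1 then has 84 − 28 = 56 days left (61 with the tolerance). The protocol window closes at entry; the SAP wording does not. Whether any event from those days reaches this study's database is a separate question, taken up in the objection.

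**Number of events.** The documents give no expected adverse event, discontinuation or rollover rates for this trial, so the days cannot be turned into subjects or events.

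**Missing onset.** Take an ongoing event with neither onset nor stop date. Protocol 16.6 makes it treatment-emergent, because nothing suggests that it stopped before treatment. SAP 6.3 gives no answer: its rule needs a stop date, and its provision for ongoing entries concerns medications only.

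**The case against.** **The protocol's own parenthesis gives only a start.** This is true, and the SAP wording is close to it. It makes an incomplete transcription plausible. But the parenthesis comes directly after the sentence that bounds the period, so it does not cancel the bound.

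**The large excesses are maxima.** This stands. Early stoppers are asked (protocol 9.7.1) or encouraged (8.4) to continue, and not all will. Protocol 7.1 also allows the follow-up visit to be timed from the last injection. That is why the last column of the table is needed.

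**The harm is limited.** SAP 10.3 specifies no between-group test, and every adverse event is listed with its onset, so late events can be traced. That lowers the stakes but does not correct the tables.

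**Stronger readings that the documents do not support.**
- A reader might infer that events after LTE entry are in fact counted, and that this pulls the groups together. LTE entrants need no follow-up visit (protocol 7.1 and 9.7), and neither document says whether their later events are recorded in this study or only in the extension. Protocol 5.3.1 calls it a nemolizumab extension, but neither document sets out its treatment assignments. Putting percentage points on the effect would need assumed event and rollover rates. An equal increment in both groups would leave the difference unchanged.
- A reader might infer that SAP 6.3 excludes undated ongoing events. It states a sufficient condition and is silent on the rest.
- It would also be wrong to say that the late events are credited to the randomized arm. Safety tables use the treatment actually received (SAP 5.2).

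**Conclusion.** The conflict is real and undeclared: the protocol closes the TEAE window and the SAP does not. Its firm consequence concerns subjects who stop drug early but remain in the study. Their excess time is 28 to 84 days after a last dose on Day 1, 0 to 56 days after Day 29 and 0 to 28 days after Day 57, depending on when last contact falls. Apart from this, the visit tolerance accounts for up to 5 days. These ranges assume doses and visits on their target days. The consequence for LTE entrants is conditional on where their events are recorded. The point should be corrected because it affects the TEAE tables, but it does not touch the primary endpoint, and no between-group bias has been shown.

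**What to change.** In SAP 10.3, define a TEAE as an adverse event with onset on or after first dose and no later than the earlier of last dose + 84 days and the LTE rollover date. List later events separately.

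In SAP 6.3, adopt the protocol rule: an event with a missing onset date, including an ongoing one with no stop date, is treatment-emergent unless data show that it stopped before first dose.

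If the sponsor prefers the open window, SAP 14 should declare and justify it.

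The cost is two SAP sentences, an upper bound in the TEAE flag with the matching missing-date rule, and a listing filter. No new data are needed.

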13.1.1 Adverse Events of Special Interest

An AESI is a noteworthy treatment-emergent event for the study drug that should be monitored closely and reported promptly. See Section 13.1.4 for reporting procedure. An AESI can be either serious or non-serious.

Based on the potential risks of nemolizumab and the risks associated with biologics (and their biosimilar equivalents) in general (ie, class effects), the following AEs will be considered AESIs:

- Injection-related reactions
 - Anaphylactic reactions
 - Acute allergic reactions requiring treatment
 - Severe injection site reaction (ie, lasting > 24 hours)
- Newly diagnosed asthma or worsening of asthma
 - More specifically, subjects with a medical history of asthma will be referred to the physician who manages their asthma when:
 - ACT score \leq 19: An ACT score \leq 19 conveys asthma that may not be adequately controlled. An AESI is reported based on the investigator's clinical judgment, including consideration of the managing physician's report.
 - PEF $<$ 80% of the predicted value: An AESI should be reported.
 - Unexpected worsening of asthma is observed or reported. An AESI is reported based on the investigator's clinical judgment.
 - Subjects without a medical history of asthma will be referred to an appropriate respiratory physician/specialist when:
 - Signs and/or symptoms suggestive of asthma have been observed or reported. An AESI is reported based on the investigator's clinical judgment of the specialist's report.

This document is confidential.

Page 82 of 133

- Respiratory assessments (eg, examination, PEF) suggest a decline in the subject's respiratory health. An AESI is reported based on the investigator's clinical judgment of the specialist's report.
- Infections
 - Any severe infection or any infection requiring treatment with parenteral antibiotics or oral antibiotics/antivirals/antifungals for > 2 weeks
 - Any confirmed or suspected COVID-19 infection
- Peripheral edema: limbs, bilateral
- Facial edema
- Elevated ALT or AST ($> 3 \times$ ULN) in combination with elevated bilirubin ($> 2 \times$ ULN)

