14.2.2.7.3	Sensitivity Analysis of Geometric Mean Concentration of Anti-tetanus IgG at Baseline and Week 16 – COVID-19 Affected Case	ITT
14.2.2.8.1	Analysis of Geometric Mean Titers of MenC SBA at Baseline and Week 16 – Imputed Values	mITT
14.2.2.8.2	Sensitivity Analysis of Geometric Mean Titers of MenC SBA at Baseline and Week 16 – Observed Case – Imputed Values	ITT
14.2.2.8.3	Sensitivity Analysis of Geometric Mean Titers of MenC SBA at Baseline and Week 16 – COVID-19 Affected Case – Imputed Values	ITT

CCI		
14.3.1.1	Overall Summary of Treatment-Emergent Adverse Events	SAF
14.3.1.2	Treatment-Emergent Adverse Events by System Organ Class and Preferred	SAF
	Term	

14.3.1.3	Treatment-Emergent Adverse Events Related to Study Drug by System Organ Class and Preferred Term	SAF
14.3.1.4	Serious Treatment-Emergent Adverse Events by System Organ Class and Preferred Term	SAF
14.3.1.5	Serious Treatment-Emergent Adverse Events Related to Study Drug by System Organ Class and Preferred Term	SAF
14.3.1.6	Treatment-Emergent Adverse Events by System Organ Class, Preferred Term and Maximum Severity	SAF
14.3.1.7	Treatment-Emergent Adverse Events Related to Study Drug by System Organ Class, Preferred Term and Maximum Severity	SAF
14.3.1.8	Treatment-Emergent Adverse Events Leading to Study Drug Withdrawal by System Organ Class and Preferred Term	SAF
14.3.1.9	Treatment-Emergent Adverse Events of Special Interest by System Organ Class and Preferred Term	SAF
14.3.1.10	Treatment-Emergent Adverse Events Leading to Temporary Interruption of Study Drug by System Organ Class and Preferred Term	SAF
14.3.1.11	Treatment-Emergent Adverse Events Leading to Study Discontinuation by System Organ Class and Preferred Term	SAF
14.3.1.12	Most Common Treatment-Emergent Adverse Events (Frequency > 5%) by Preferred Term	SAF
14.3.1.13	Adjudicated Treatment Emergent Adverse Events (TEAEs) by SOC and PT	SAF
14.3.1.14	Treatment Emergent Adverse Events (TEAEs) of Asthma and Asthma related events reported by Investigator with Adjudication Outcome by IAC	SAF
14.3.1.15	Confirmed Adjudicated Treatment Emergent Adverse Events (TEAEs) by SOC, PT and Maximum Severity	SAF
14.3.2.1	Listing of Serious Adverse Events	SAF
14.3.2.2	Listing of Adverse Events Leading to Study Drug Withdrawal	SAF
14.3.2.3	Listing of Adverse Events of Special Interest	SAF
14.3.2.4	Listing of Adjudicated Asthma Treatment-Emergent Adverse Events (TEAEs)	SAF

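### The AESI table has no rows for the protocol's AESI categories, so categories spanning several terms, and the AESI total without COVID-19, have no planned subject count by arm

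*SAP*

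**What the plan says.** Protocol Section 13.1.1 opens its list with "the following AEs will be considered AESIs" and then names six categories:

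1. Injection-related reactions, in three subtypes: anaphylaxis, "Acute allergic reactions requiring treatment", and severe injection site reaction.
2. "Newly diagnosed asthma or worsening of asthma".
3. Infections, in two parts: "Any severe infection or any infection requiring treatment with parenteral antibiotics or oral antibiotics/antivirals/antifungals for > 2 weeks", and COVID-19, whether confirmed or only suspected.
4. Bilateral peripheral edema.
5. Facial edema.
6. Raised ALT or AST together with raised bilirubin.

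For the analysis, Protocol Section 16.6 says that treatment-emergent AESIs, among other events, will be "included in incidence tables, summarized by System Organ Class (SOC) and Preferred Term (PT"). SAP Section 10.3 repeats this as "The total number and incidence of TEAEs of special interest by SOC and PT", and the SAP table index lists Table 14.3.1.9, "Treatment-Emergent Adverse Events of Special Interest by System Organ Class and Preferred Term". None of Tables 14.3.1.1 to 14.3.1.15 is organized by the categories of Protocol Section 13.1.1.

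The counting rule in SAP Section 10.3 is "Subjects who have multiple events in the same SOC and the same PT within each SOC will be counted only once". It works per SOC and per PT. There is no matching rule for an AESI category.

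The overall summary in SAP Section 10.3 gives subjects with any treatment-emergent AESI and, as a separate item, subjects with COVID-19. Asthma has Tables 14.3.1.13 to 14.3.1.15, based on adjudication. AESIs are also listed by subject (14.3.2.3).

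**The concern.** The protocol chose its AESIs as clinical risks, and several rest on criteria that a coded term does not carry: that treatment was needed, how long anti-infectives were given, that edema was bilateral, or that two liver abnormalities occurred together. A display by SOC and PT answers a different question. If one category is coded to several terms, its subjects are spread over several rows, and adding the rows counts some subjects twice.

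COVID-19 raises a related problem. It is an AESI by definition, so it enters the any-AESI line, and it is an infection, so it can be expected to share a SOC with the other infection AESIs. A reader who wants to compare the arms on AESIs other than COVID-19 has no planned number.

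What is at stake is the clarity of a secondary safety endpoint. Protocol Section 6.2.2.3 includes AESIs in the incidence and severity of adverse events. No test, sample size or primary conclusion is affected.

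**Working it through.** The plan states no figure on this point, so there is none to reproduce. The check sets the categories against the planned outputs and then works out what a reader could recover.

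**Step 1. Coverage.** Categories are from Protocol Section 13.1.1; outputs are from SAP Sections 10.3 and 17.

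| Category | Subject count by arm available from planned outputs |
|---|---|
| Injection-related reactions | No category row; three subtypes, so several PTs and possibly several SOCs |
| Asthma | Adjudication tables 14.3.1.13 to 14.3.1.15 |
| Infections other than COVID-19 | No row; many possible PTs, SOC expected to be shared with COVID-19 |
| COVID-19 | Own line in the overall summary |
| Peripheral edema | PT row, if coded to one PT |
| Facial edema | PT row, if coded to one PT |
| Combined liver criterion | No row in the AESI table; the criteria in SAP Section 20.2 are not in the public text |

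The documents give no mapping of categories to PTs. The gap is therefore clear for the first and third rows and cannot be settled for edema and liver.

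**Step 2. A category spread over several rows.** Assume three PTs in three different SOCs, 2 subjects each, in an arm of 123 (arm size from Protocol Section 16.9; the counts are illustrative).

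- Full overlap: 2 subjects, 2/123 = 1.6%.
- No overlap: 2 + 2 + 2 = 6 subjects, 6/123 = 4.9%.

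The table shows three rows of 1.6%, and the category incidence lies anywhere from 1.6% to 4.9%. If all three PTs fell in one SOC that held no other AESI, the SOC row would give the exact count and there would be no gap.

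**Step 3. Removing COVID-19 by subtraction.** Let A be subjects with any AESI, C those with COVID-19, B those with both COVID-19 and another AESI, and N those with an AESI other than COVID-19. Then N = A − C + B, with B between 0 and C. The plan reports A and C but not B. With assumed A = 20 and C = 12:

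- B = 0: N = 20 − 12 = 8, or 8/123 = 6.5%.
- B = 12: N = 20 − 12 + 12 = 20, or 20/123 = 16.3%.

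**Step 4. What COVID-19 does to the pooled line.** Let p be the rate of other AESIs and c the COVID-19 rate. If the two are independent and c is equal in both arms, the any-AESI rate is 1 − (1 − p)(1 − c). Purely for illustration, take p from the earlier peripheral edema rates in Protocol Section 5.3.1: 3.6% on placebo and 7% at 30 mg. The values of c are assumptions.

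| c | Placebo | 30 mg | Difference (points) | Ratio |
|---|---|---|---|---|
| 0% | 3.6% | 7.0% | 3.4 | 1.94 |
| 5% | 8.4% | 11.7% | 3.2 | 1.38 |
| 10% | 13.2% | 16.3% | 3.1 | 1.23 |
| 15% | 18.1% | 21.0% | 2.9 | 1.16 |

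The ratio falls quickly. The difference falls little, but it sits on a larger background rate.

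**The case against.** The strongest reply is that the SAP does what the protocol asks. Protocol Section 16.6 specifies SOC and PT, and the safety endpoint does not call for incidence by category. This stands: there is no contradiction and no departure.

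Second, a reader might infer that subject-level incidence of most named risks is never produced. The documents do not support that. Table 14.3.1.9 holds AESIs only, and its SOC and PT rows are de-duplicated subject counts, so a category coded to one PT, or alone in its SOC, is readable. Without a PT mapping, the number of affected categories cannot be stated.

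Third, other outputs cover part of the ground. COVID-19 has its own summary line. Asthma has adjudication tables, with summaries of low asthma control scores and low peak flow besides. Liver tests have shift tables, boxplots and proportions with potentially clinically significant values, and a combined liver count under SAP Section 20.2 cannot be ruled out. These points stand, but none of them supplies a count for injection-related reactions or for infections other than COVID-19.

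Fourth, a reader might infer that COVID-19 will dominate the AESI total. The documents give no COVID-19 rate, so this remains conditional.

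Finally, category counts could be rebuilt from the AESI listing. They could, but the grouping would then not be pre-specified and might be decided with treatment known.

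**Conclusion.** The point holds as a modest reporting gap. Injection-related reactions, as far as they span several PTs or SOCs, and infections other than COVID-19 have no planned subject-level incidence by arm. No AESI total excludes COVID-19, and none can be derived from the two summary lines, because a subject may have both kinds of event.

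The illustrations (1.6% to 4.9% for one category; 8 to 20 subjects after removing COVID-19; a ratio falling from 1.94 to 1.16) rest on assumed counts and rates. They show how uncertain the reading could be and do not forecast this trial. The statement about infections also assumes that COVID-19 and other infections are coded to the same SOC, since the documents print no mapping.

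Safety is summarized descriptively and the arms can still be compared on every SOC and PT row, so this is an inexpensive improvement and not a flaw that threatens a conclusion.

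**What to change.** In SAP Section 10.3 and the shell of Table 14.3.1.9:

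- Add subject n (%) rows by arm for each category and sub-category of Protocol Section 13.1.1, above the PT level, counting a subject once per category.
- Split infections into COVID-19 and other.
- Add a row for any AESI excluding COVID-19, and repeat it in the overall summary.

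The SOC and PT display can stay, so Protocol Section 16.6 is still met.

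The cost is a little extra programming on one table, one added summary row, and a mapping of AESIs to categories. Protocol Section 13.1.4 mentions an AESI form but does not say that it records the category, so the mapping may have to be built from the adverse event data. It should be fixed at the blind data review described in Protocol Section 16, before unblinding. No test, sample size or protocol definition changes.
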